5.1.3 ALLOCATION TO FOLLOW UP

For patients who are enrolled, the IVUS-NIRS images will be submitted to the NIRS Core Laboratory within 5 business days of collection and enrollment. The NIRS Core Lab will then assess the totality of NIRS findings, excluding locations and 10 mm borders of locations that underwent PCI, to establish the patient level max 4mm LCBI of all scanned segments. The NIRS Core Lab determination that the per patient max 4mm LCBI is below 250 will indicate that the patient will be randomized to follow-up or no follow-up. Patients with values above > or = to 250 will all receive follow-up per figure 1. The NIRS Core Lab will provide notification to the site prior to the 60 day follow up time interval to indicate to the sites which patients require follow up. The patient will be allocated as below:

- Patients with a max 4mm LCBI of all scanned segment ≥ 250 will be followed for a 2 year period as described in section 5.1.3.
- Patients with a max 4mm LCBI of all scanned segment < 250 will be randomized to follow up or no follow up beyond hospital discharge. Patients randomized (in a 1:1 fashion) to follow up will be followed for a 2 year period as described in section 5.1.3. The allocation will occur within the electronic case report form system and will take into consideration the site and have a set block size to help mitigate unequal allocation by site. Patient allocated to no follow up beyond hospital discharge will only have data collected through hospitalization within the electronic case report form.

The NIRS findings from the Index Non-culprit Artery details including the Core Lab determined patient-level max 4mm LCBI will be blinded to the clinical site.

5.1.4 FOLLOW UP

Follow up:

The site will be notified prior to the 60 day follow up window whether or not the patient requires follow up per the algorithm listed in section 5.1.2.2, Allocation to Follow up. The NIRS Core Lab will notify the enrolling site of the follow up allocation without unblinding the max 4mm LCBI per patient value.

Patients allocated to the 24 month follow up group will undergo clinic or telephone contact or medical record review at 60 days (± 14 days), 6 months (± 14 days), 12 months (± 30 days) and 24 (± 30 days) months. The follow up will include the review for the occurrence of NC-MACE following hospital discharge from the Index Procedure or the last follow up. If the lipid profile was clinically evaluated following hospital discharge from the Index Procedure or the last follow up, these values will be recorded within the electronic case report form.

Patients will have essential data collected at the time of index enrollment. These data will be collected by an electronic data capture system.

NC-MACE Occurrence:

Once an event has been identified by the coordinator, additional source documentation regarding the event will be collected. These data will be submitted to the Clinical Event Committee for adjudication to confirm that a NC-MACE has occurred, and, if possible, to identify the site of the Follow up Culprit Lesion causing the event. Such supporting documents will include, but not be limited to:

Death certificates, autopsy reports, discharge summaries, relevant progress notes from rehospitalizations for ischemia or angina, catheterization reports, surgical reports, angiograms (films), re-imaging (films), etc.

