The LRP Study is a multicenter, prospective registry of patients with stable ischemic heart disease or a stabilized acute coronary syndrome (ACS) examined with angiography and IVUS-NIRS imaging for one or more suspected culprit lesions. After successful PCI of all angiographically flow-limiting lesions, intravascular imaging with the combined IVUS-NIRS catheter will be performed in all three coronary arteries if possible. Successful imaging of at least two vessels and a total of 50 mm of coronary artery is required for enrollment. All enrolled patients with a large LRP as detected by NIRS will be contacted at 2,6,12 and 24 months by phone to determine if a new coronary event has occurred. A randomly selected half of the patients with a small, or no, LRP will receive an identical follow-up. The origin of any new event will be determined by the follow-up angiography performed for clinical indications. The location of new culprit lesions will be identified and compared to the baseline NIRS findings in a central angiographic and NIRS-IVUS core laboratory located at MedStar.

Estimated number of subjects:

The goal is to enroll 9000 patients in the LRP Study. On the basis of the findings in the PROSPECT Study and the NIRS STEMI findings it is not expected that all 9,000 will be required to demonstrate successful prediction of coronary events with IVUS-NIRS imaging. If and when the goal of prediction is reached, the study will transition to a study of systemic and/or regional therapy of vulnerable patients and plaques.

Patient Enrollment and Procedure Overview:

Patients with stable ischemic heart disease or an ACS and planned coronary angiography in whom IVUS-NIRS imaging is likely to be performed will be asked to provide their consent for participation in the study. Angiography and PCI will be performed as clinically indicated. Unblinded NIRS IVUS imaging will be performed in the vessel, or vessels, containing a single or multiple suspected culprit lesions. Imaging for research purposes will begin in non-culprit vessels after all clinically indicated PCI has been performed. If a staged procedure is required to achieve revascularization of all lesions detected by angiography, the patient is not enrolled until after the staged procedure is successful and uncomplicated.

Imaging results in an artery not suspected to be a culprit will be blinded for NIRS, but not for IVUS.

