5. Subject with ejection fraction (EF) <30%.
6. Subject pacemaker dependent/paced rhythm.
7. Subject pregnant and lactating.
8. Any other factor that the investigator feels would put the patient at increased risk or otherwise make the patient unsuitable for participation in the protocol

9. Patients undergoing performance of PCI in all three major vessels during the index PCI.

Study follow-up:

All enrolled patients with a large LRP (Maximum Lipid Core Burden Index > 250 in 4 mm) will be contacted by phone by the study coordinator for each clinical site at 2, 6, 12 and 24 months to determine if a new coronary event has occurred. A randomly selected half of the patients with a small, or no LRP (Max 4mm LCBI < 250) will receive an identical follow-up. The determination of the need for follow-up will be made by the NIRS core lab after unblinding of the NIRS data and communicated to the clinical site prior to the 2 month follow-up.

The origin of any new event will be determined by the follow-up angiography performed for clinical indications. Clinical and imaging data for any follow-up event will be sent to the central angiographic and IVUS/NIRS core laboratory located at MedStar. The location of new culprit lesions will be identified by a clinical events committee (blinded to the baseline NIRS results), and compared to the baseline NIRS findings by the core laboratory.

Endpoints:

The primary outcome variable is Non-Index Culprit Lesion related Major Adverse Cardiac Events (NC-MACE) defined as the composite of:

- cardiac death,
- cardiac arrest,
- non-fatal myocardial infarction (MI),
- acute coronary syndrome,
- revascularization by CABG or PCI,
- rehospitalization for progressive angina, adjudicated to a non- index culprit lesion secondary to significant fixed, non-reversible (not-spasm related) lesion progression of more than 20% from the baseline study (confirmed by either serial angiography or by necropsy).

Statistical methods:

The study will test two primary hypotheses:

1)The Vulnerable Patient Hypothesis -- During a 24-month follow-up after IVUS-NIRS imaging, there will be an association between the baseline value of max 4mm LCBI (over all coronary artery segments included in the analysis) and the incidence of non- index culprit MACE events.

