4.1.2 EXCLUSION CRITERIA

Subjects must meet none of the following exclusion criteria prior to enrollment:

General Exclusion Criteria

1. Unstable patients (STEMI within the prior 24 hours; cardiogenic shock, hypotension needing inotropes, hypoxia needing intubation, and IABP) and patients that had a procedural complication (coronary dissection, perforation or a complication that would necessitate immediate-unplanned revascularization) during index PCI procedure.
2. History of CABG or planned CABG within 6 months following NIRS-IVUS imaging.
3. Patient has additional lesion(s) that needs a staged PCI.
4. Subject life expectancy is less than 2 years at time of index catheterization.
5. Subject with ejection fraction (EF) <30%.
6. Subject pacemaker dependent/paced rhythm.
7. Subject pregnant and lactating.
8. Any other factor that the investigator feels would put the patient at increased risk or otherwise make the patient unsuitable for participation in the protocol.
9. Patients undergoing performance of PCI in all three major vessels during the index PCI.

4.2 REVIEW OF CHEMOGRAM TO DETERMINE PROTOCOL FOR FOLLOW-UP DEPENDING ON THE PRESENCE OR ABSENCE OF A LARGE LRP

At the end of the index procedure the chemogram (the NIRS findings output) data for both the Suspected Index Culprit Lesion or Lesions (unblinded) and Index Non-culprit (blinded) Arteries will be submitted to the NIRS Core Laboratory for evaluation. The Core Lab will review the chemogram to determine if a large LRP is present in an area that:

- 1) had not undergone PCI in the past,
- 2) did not undergo PCI at the time of the index procedure.

Areas that have undergone PCI (stent, balloon or other device) plus a 5 mm border on either side of the intervened area will be excluded from analysis.

A "large LRP" will be defined as a 4mm segment within the eligible area with an LCBI \geq 250.

The Large LRP Group: All patients with a large LRP will be followed with a phone inquiry at 2,6,12 and 24 months post enrollment.

The Small or No LRP Group: Of this group, 50% will be randomly assigned (in a 1:1 fashion) to be followed with a phone inquiry at 2,6,12 and 24 months post enrollment.

The follow-up status for each patient will be determined by the core lab and communicated to the site coordinator prior to the 2 month follow-up window for the call. The clinical site will remain blinded to the NIRS findings, as will the clinical events committee.

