6.2 SAMPLE SIZE CONSIDERATIONS

A total of 9,000 patients will be enrolled with multi-vessel scans. It is expected based on the PROSPECT Study that at least 720 patients (8%) will experience a NC-MACE event. We expect to find approximately 3,000 patients with large LRP (max 4mm LCBI \geq 250). All 3,000 of these patients will be followed with phone calls for 2 years to identify those who have an event. We expect to observe at least 300 events in this group. From the 6,000 with no or small LRP, a random sample of 3,000 patients will also be followed to determine their event rate, and to examine with IVUS and angiograms those in whom events occur. Of the approximately 2,700 patients with large LRP who do not have an event, a 300 person sample will be selected for IVUS and angiographic analysis to investigate characteristics of the yellow spots that did not lead to events.

Vulnerable Patient Analysis

For hypothesis 1, we will test the hypothesis that there will be no association between the baseline value of max 4mm LCBI (over the entire area scanned) and the incidence of NC-MACE.

In PROSPECT registry results, the 24-month cumulative incidence of NC-MACE in patients was approximately 10%. Subsequent STEMI literature indicates that patients with large LRP will have a higher rate than that observed in PROSPECT.

For the power calculations below, we assumed 6,000 evaluable patients, an event rate between 4 and 8% in the overall LRP study, and a two-sided alpha of 0.05 with a standard deviation of 100 for max 4mm LCBI. Table 2

provides values for the power of the study to detect the following effect sizes: hazard ratio of 1.18, 1.20, and 1.22 per 100 unit increase in max 4mm LCBI (calculated in PASS 12). These results demonstrate that the study will have 80% power to detect a minimal effect size of 1.18 per 100 unit increase in the max 4mm LCBI with 6,000 patients and an overall cumulative incidence of 5% at 24 months. As described in section 5.3, interim analyses will be performed at 6 month intervals.

Table 2: Hypothesis 1: Power Calculation for Vulnerable Patient Hypothesis

2 Year cumulative incidence overall, patient level	Relative Risk per 100 unit increase in max 4mm LCBI		
	1.18	1.20	1.22
8%	0.95	0.98	0.99
7%	0.92	0.96	0.98
6%	0.88	0.93	0.97
5%	0.82	0.88	0.93
4%	0.73	0.81	0.87

Vulnerable Plaque Analysis

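### Section 5.1.4 allows any follow-up, including the closing 24-month one, to be done by medical record review alone, while the synopsis, 4.2 and 6.2 specify phone contact; events treated elsewhere can be missed

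*Combined protocol and SAP*

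**What the plan says.** The operational follow-up section, 5.1.4, states that patients allocated to follow-up "will undergo clinic or telephone contact or medical record review at 60 days" and so on to 24 months. The three modes are joined by *or*. Record review is not reserved for patients who cannot be reached, and the section does not say whose records are to be reviewed.

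Elsewhere the mode is the telephone:

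- Synopsis, Methodology: large-LRP patients "will be contacted at 2,6,12 and 24 months by phone to determine if a new coronary event has occurred", with identical follow-up for the sampled half of the others.
- Synopsis, Study follow-up: patients "will be contacted by phone by the study coordinator for each clinical site at 2, 6, 12 and 24 months".
- Section 4.2, large-LRP group: "All patients with a large LRP will be followed with a phone inquiry at 2,6,12 and 24 months post enrollment". The sampled small or no LRP group is likewise "to be followed with a phone inquiry at 2,6,12 and 24 months post enrollment".
- Section 6.2: "All 3,000 of these patients will be followed with phone calls for 2 years to identify those who have an event".

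Section 5.1.4 also sets the trigger for gathering evidence: "Once an event has been identified by the coordinator, additional source documentation regarding the event will be collected". Section 6.1 plans time-to-event analyses but gives no rule for censoring or for the status of a patient who was not directly contacted. No separate SAP text is among the documents.

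**The concern.** NC-MACE is the whole outcome of this registry. Table 1 rules out protocol-driven repeat catheterization, so an event enters the data only if the coordinator learns of it. A chart may hold nothing about an infarction, a PCI or a death at another hospital, and a chart without an entry looks the same as a patient without an event. The events committee cannot recover an event that never reaches it. Table 1 schedules no contact between 12 and 24 months, so a chart-only closing check can leave a year in which nobody has asked the patient anything.

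If such patients are carried to 24 months as event-free, the 24-month incidence is understated, along with measures built on absolute risk such as the net reclassification improvement. Both primary hypotheses also lose events. Section 6.2 leaves little room for this: its 6,000 evaluable patients are the entire planned follow-up cohort (3,000 plus 3,000, section 4.2), with no stated allowance for loss.

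**Working it through.** **1. Reproduce the plan's power.** Inputs from section 6.2: 6,000 patients, two-sided alpha 0.05, SD 100 LCBI units, hazard ratio 1.18 per 100 units, incidence 4% to 8%. For a proportional hazards model with one continuous covariate, with the SD equal to one 100-unit step,

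power = Φ(√D × ln HR − 1.96), where D = 6,000 × incidence.

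At 5%, D = 300 and √300 × ln 1.18 − 1.96 = 0.91, so power is 0.818 (Table 2: 0.82). At 8%, D = 480 and power is 0.952 (Table 2: 0.95). All 15 cells of Table 2 reproduce to rounding. The plan's power figures are not in dispute.

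**2. Share of events that could be missed.** The documents give no figures, so these are assumptions: 10% to 50% of patients closed by chart review only, and 20% to 40% of their events treated elsewhere and absent from the chart.

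- *Chart-only at 24 months, direct contact up to 12 months.* Only events after month 12 are exposed, about half at a constant hazard. Low end: 0.10 × 0.20 × 0.5 = 1%. High end: 0.50 × 0.40 × 0.5 = 10%.
- *Chart-only at all four contacts.* All events are exposed: 0.10 × 0.20 = 2% to 0.50 × 0.40 = 20%.

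In the first scenario a true incidence of 5% would be estimated at about 5% × 0.99 = 4.95% down to 5% × 0.90 = 4.5%.

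**3. Effect on power at hazard ratio 1.18.**

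| Events missed | 5% incidence: events, power | 8% incidence: events, power |
|---|---|---|
| 0% | 300, 0.82 | 480, 0.95 |
| 10% | 270, 0.78 | 432, 0.93 |
| 20% | 240, 0.73 | 384, 0.90 |

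Power of 80% needs (1.960 + 0.842)² / (ln 1.18)² ≈ 287 events. At 5% incidence the margin is therefore 13 of 300 events, about 4%. For Hypothesis 2, Table 3 gives the same 0.82 at 24,000 × 1.25% = 300 segment-level events, so the same loss of events has the same effect under the plan's own method.

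**4. Direction of the error.** If misses are unrelated to LCBI, detected events fall by the same proportion at every exposure level. For a rare outcome the hazard ratio is then roughly unchanged. The AUC barely moves, because even a 20% loss at 5% incidence puts only 0.20 × 5% = 1% of patients in the wrong outcome group. What suffers is absolute incidence and power.

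**5. A censoring rule that would make things worse.** One might censor record-reviewed patients without events at their last direct contact but still count events found in their records. With chart-only share *c* and treated-elsewhere share *e*, the year-2 hazard is then multiplied by about [(1 − c) + c(1 − e)] / (1 − c). For c = 0.10, e = 0.40 this is 0.96/0.90 = 1.07; for c = 0.50, e = 0.20 it is 0.90/0.50 = 1.80. The true cumulative hazard at 5% incidence is −ln 0.95 = 0.0513, or 0.0256 per year. The estimate becomes 1 − exp(−0.0256 × 2.07) ≈ 5.2% to 1 − exp(−0.0256 × 2.80) ≈ 6.9%. At its worst that is an error of almost 2 points, against at most 0.5 points in step 2.

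**The case against.** Section 4.2 is body text as binding as 5.1.4, and section 12.4 says the protocol is to be followed exactly. A site that never telephones departs from 4.2, so wide use of chart-only follow-up is not what the plan intends. Nor does 5.1.4 limit the review to the enrolling hospital's records or say that a silent chart means no event. This stands: the loss of events is an inference about what the wording permits, not something the documents show will happen. It does not remove the contradiction, because a site that relies on 5.1.4 is also following the protocol and no other section closes the gap.

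The power cost is also modest if the higher incidence holds. Section 6.2 expects at least 8% to have an event, and there power stays at 0.90 even with 20% of events lost. This stands too.

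A reader might infer more: that sites will pursue patients known to have lipid harder, and so bias the hazard ratio. The route exists, because culprit-artery NIRS is unblinded and untreated portions of that artery count towards the exposure. But sites are blinded to non-culprit NIRS and to the patient-level max 4mm LCBI (section 5.1.3), and nothing in the documents links mode of contact to NIRS results. Section 6.1 also plans to examine whether the association differs between blinded and unblinded recordings, which is a partial check. Differential loss is possible but not shown.

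**Conclusion.** The contradiction is clear and worth correcting. As written, 5.1.4 lets a chart review alone close a patient's follow-up, four other places specify the telephone, and nothing recovers an event the coordinator never identifies. The likely harm is an understated 24-month incidence and some lost power.

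On the assumed inputs, a chart-only 24-month check misses about 1-10% of events. The 2-20% range needs all four contacts to be chart-only, which is hard to square with a plan that specifies phone contact in four places. At hazard ratio 1.18, power goes from 0.82 to 0.78 with 10% lost at 5% incidence, and from 0.95 to 0.93 at 8%. These figures rest on the assumed shares, a constant hazard and a single-look 0.05 test as in Table 2. The documents do not support saying that events will be missed, that the hazard ratio is biased, or that the AUC is materially changed.

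**What to change.** 1. Reconcile 5.1.4 with the synopsis, 4.2 and 6.2: make direct contact with the patient or a family member, by phone or in clinic, the required follow-up at each time point.
2. Keep record review for source documents and as a back-up after failed contact.
3. Record the mode of each contact in the eCRF.
4. State a symmetric rule for events and event-free time. For example, in the main analysis censor every unreached patient at last direct contact whatever later records show, and in a sensitivity analysis count both events and event-free time from record review. Do not count events from records while refusing the matching event-free time (step 5 of the working).

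The cost is protocol wording and one eCRF field; phone contact is already planned elsewhere. The main-analysis rule sets aside some documented events and shortens some follow-up. It also assumes that being unreached is unrelated to having had an event, which is doubtful for deaths. Accepting contact with a family member limits that problem, and the sensitivity analysis shows how much it matters.

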5.1 STUDY ASSESSMENTS AND PROCEDURES

5.1.1 STUDY SCHEDULE

Table 1: Schedule of Contacts

	Index	60 days (± 14 days)	6 months (± 14 days)	12 months (± 14 days)	24 months (± 30 days)
Patient Data*	X				
Procedural details	X				
TVC Imaging	X				
Angiogram submission [§]	X	X [§]	X [§]	X [§]	X [§]
NIRS/IVUS submission [§]	X	X [§]	X [§]	X [§]	X [§]
Adverse Events	X				
MACE	X	X	X	X	X

*Demographics, medical history and risk factor review; [§]angiograms and NIRS IVUS data will be collected if MACE occur (no protocol driven follow up catheterization or protocol driven TVC will be performed). Patients with no large LRP who are not randomly assigned to the 2 year follow-up will still have their baseline data and procedural data recorded and submitted for analysis.

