10.2 CLINICAL EVENTS ADJUDICATION COMMITTEE

A Clinical Events Committee (CEC) consisting of at least three members will be established to review and adjudicate all clinical endpoints as defined in the protocol. The CEC will be independent from the study Sponsor. The primary mission of the Committee is to audit and review any major clinical event that occur within the follow up period for the purpose of accurate classification. The Committee will meet on an on-going basis as necessary to assure timely review of the data. Endpoint adjudication will be transmitted to the Data Analysis Center at MedStar for adjustment of the final database as necessary. The CEC will be blinded to all the Index IVUS-NIRS findings throughout the duration of the study.

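### The blinding of the Clinical Events Committee is spelled out only for index imaging, so follow-up NIRS in an event file could inform the choice of culprit lesion that defines the H2 outcome

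*Combined protocol and SAP*

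**What the plan says.** **The CEC's task.** Section 5.1.4 sends event documents to the CEC to confirm NC-MACE and, if possible, "to identify the site of the Follow up Culprit Lesion causing the event". The listed documents include "catheterization reports, surgical reports, angiograms (films), re-imaging (films), etc". The list is open-ended and states no masking step.

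**Imaging at an event.** The Table 1 footnote in section 5.1.1 reads: "angiograms and NIRS IVUS data will be collected if MACE occur (no protocol driven follow up catheterization or protocol driven TVC will be performed". Follow-up NIRS is therefore foreseen, but only when the site chose to perform it.

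**Blinding of the CEC.** There are three statements:
- Synopsis, Study follow-up: culprit location is "identified by a clinical events committee (blinded to the baseline NIRS results").
- Section 10.2: "The CEC will be blinded to all the Index IVUS-NIRS findings throughout the duration of the study".
- Section 4.2: "The clinical site will remain blinded to the NIRS findings, as will the clinical events committee". This has no time limit, but it closes a section about the index chemogram.

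**Who locates the culprit.** The synopsis gives two answers. Its Methodology paragraph places both the location of new culprits and their comparison with baseline NIRS in the core laboratory. Its Study follow-up paragraph gives location to the CEC and comparison to the core laboratory, and routes follow-up event imaging to that laboratory.

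**The concern.** H2 asks whether the max 4mm LCBI of a coronary segment predicts a later culprit in that same segment (section 6.1). The location call is thus the outcome itself. A reader who sees a lipid map while choosing between candidate lesions may favour the lipid-rich one. If follow-up lipid resembles baseline lipid, outcome assignment then depends on exposure, and the error runs away from the null.

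Two features of the protocol make this more than theoretical. Section 2.1 reports that a max 4mm LCBI above 400 discriminated STEMI culprit lesions well from the rest of the same artery, so adjudicators have reason to treat lipid as a culprit marker. Section 2.1.1 accepts that visible NIRS can bias treatment and symptom reporting, and blinds the sites to non-culprit arteries for that reason. The event file lacks the matching safeguard.

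**Working it through.** **1. The plan's own figure.** Section 6.2 takes 24,000 segments from 6,000 patients (4 per patient), 1.25% incidence, SD 100 and two-sided alpha 0.05.
- Events: 24,000 × 0.0125 = 300.
- Power for a hazard ratio (HR) of 1.18 per 100 units: Φ(√300 × ln 1.18 − 1.960) = Φ(2.867 − 1.960) = Φ(0.907) = 0.82, as in Table 3.

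**2. Bias model.** Assume that H2 is null, that exposure is normal with SD 100, that within-patient correlation is 0.3, and that follow-up lipid ranks a patient's segments as baseline does. In a share *f* of the 300 events, the CEC picks the most lipid-rich of *k* candidate segments. Otherwise location is unrelated to lipid. The documents give neither *f* nor the correlation.

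For a normal exposure, the log HR per SD is approximately the shift in mean exposure among event segments:

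ln HR ≈ *f* × E(max of *k* standard normals) × √(1 − 0.3)

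- *k* = 2: 0.564 × 0.837 = 0.472.
- *k* = 4: 1.03 × 0.837 = 0.861.

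The test statistic has mean ln HR × √300.

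**3. Which *k*.** Section 6.2 spreads the minimum of 4 segments over at least 2 arteries, which is about 2 per artery if split evenly. A repeat pullback of one artery fits *k* = 2. Choosing among all four segments needs repeat imaging of every scanned artery. A fully scanned artery with three segments lies between.

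**4. Worked case, *f* = 10%.**
- *k* = 2: ln HR = 0.0472, HR 1.05. Mean z = 0.0472 × 17.32 = 0.82. Two-sided rejection at ±1.96 is about 13%.
- *k* = 4: ln HR = 0.0861, HR 1.09. Mean z = 0.0861 × 17.32 = 1.49. Rejection is about 32%.

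| Share swayed | HR, *k* = 2 | Rejection | HR, *k* = 4 | Rejection |
|---|---|---|---|---|
| 2% | 1.01 | 5.3% | 1.02 | about 6% |
| 5% | 1.02 | 6.9% | 1.04 | about 12% |
| 10% | 1.05 | 13% | 1.09 | about 32% |

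Simulation of the four-segment case at 10% agrees: HR 1.09 and rejection 0.32. With correlation varied from 0 to 0.5, the ranges are HR 1.08 to 1.11 and rejection 0.24 to 0.44. With no calls swayed, simulated rejection is about 0.05.

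**5. Share needed to produce the design effect from bias alone.** ln 1.18 = 0.1655.
- *k* = 2: 0.1655 / 0.472 = 35% of all events.
- *k* = 4: 0.1655 / 0.861 = 19%.

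**6. Planned test level.** Section 6.3 tests the final hypotheses at the Pocock interim level. Reviews every six months from December 2014 to December 2016 make five, plus the final. With equal spacing assumed, the critical value is about 2.45, a nominal level of 1.4%. At *f* = 10%, rejection at the final look is then about 5% (*k* = 2) or 17% (*k* = 4).

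**The case against.** A reader might infer that the CEC is blinded to index NIRS alone and will routinely see the lipid map. The documents do not support that. Section 10.2 covers index IVUS as well as NIRS, and section 4.2 is not limited in time. Section 5.1.4 is a generic list that does not say the re-imaging is NIRS. Repeat imaging is not protocol-driven, and the synopsis routes event imaging to the core laboratory. A report quoting the unblinded NIRS of the index culprit artery is already barred from the CEC by section 10.2; only the redaction step is missing. What the CEC might see on film is the follow-up map, and bias needs that to track baseline.

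A reader might also infer that the H2 association could be manufactured outright. That needs about 35% of all events swayed in the same-artery case. The swayed share is itself a product: events re-imaged with NIRS, times those with an unclear culprit, times those resolved toward lipid. The documents give none of the three. The requirement of more than 20% progression on serial angiography or necropsy also narrows the choice, although it is unclear whether it applies to every endpoint component, and it does not rank two lesions that both progressed. An effect on H1, through the choice between a treated site and a new site, is conceivable but has not been quantified, and no claim about it is made here.

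These objections limit the size and frequency of the problem. They do not supply a masking rule, and none of the three blinding statements expressly addresses follow-up NIRS. The section 6.1 comparison of blinded with unblinded recordings concerns index imaging and does not fill the gap.

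**Conclusion.** The gap is real but conditional. It applies to events where the site repeated NIRS or where a report mentions it. For those events, the plan as written allows information correlated with the exposure to inform the H2 outcome, in the anti-conservative direction.

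Its size cannot be fixed from the documents. At an assumed 10% of calls swayed, the spurious HR runs from about 1.05 with two candidate segments to 1.09 with four, and nominal rejection from about 13% to one in three. At 2% it is negligible. These figures assume a true null, 300 located events, correlation 0.3 and follow-up lipid that ranks segments as baseline does. Weaker tracking shrinks the bias, and the stricter Pocock level lowers the rejection rates. This should be fixed as a cheap improvement. It is not a defect that by itself invalidates H2.

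**What to change.** - In sections 5.1.4 and 10.2, and in the CEC charter, extend CEC blinding to all NIRS data, index and follow-up.
- Before a file goes to the CEC, remove the chemogram and LCBI display from re-imaging films and redact NIRS wording from index and follow-up reports.
- Have the CEC fix and lock the culprit site from angiography, with follow-up greyscale IVUS if needed, before the core laboratory uses follow-up NIRS.
- Align the two synopsis paragraphs (Methodology and Study follow-up) with sections 4.2, 5.1.4 and 10.2 on who locates the culprit and what they may see.
- As a check, add an H2 sensitivity analysis that excludes events with follow-up NIRS.

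The cost is a redaction step for each event file and a wording change. No extra reader is needed, and the design power of 0.82 is unchanged. The CEC loses NIRS as an aid in a few unclear cases. These can be recorded as site not determined, which section 5.1.4 already allows for by asking for the site only where possible. The change should precede the first adjudication, because blinding cannot be restored once the maps have been seen.
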